 - ii. The protocol will be described to the patient; this description will include an overview of student events they already completed, cover in detail the study intervention and any remaining/future study procedures/events, and cover the risks associated with participation.
 - iii. We will assure study subjects that participation is voluntary and that the decision to continue their participation will have no impact on their current or future care.
 - iv. A copy of the consent document will be provided to the patient.
- f. **Timeline of Study Activities (Fig 2):** Patients will be enrolled within 30 hours of hospital admission and before 12:00 on the day of enrollment which is designated “Study Day 1 (D1).” Actigraphy, delirium monitoring, and light measurement (part of feasibility) will start no later than 12:00 on D1. Actigraphy and light measurement will continue until D5 or MICU discharge whichever is longer. If the patient is discharged from the hospital prior to day 5, all study activities stop upon hospital discharge. Study activities will continue if/when the patient is transferred to the general medical floor if the patient completes at least D2 (13:00) in the MICU. Delirium monitoring will occur until D30 or hospital discharge.

[figure not shown]

Figure 2: Study activities timeline.

APPROACH TO AIMS

Aim 1: Determine the association between ICU day-night light patterns and circadian abnormalities (i.e., circadian misalignment and decreased circadian amplitude).

Rationale: Aim 1 will test our hypothesis that non-circadian ICU light patterns are associated with increased circadian abnormalities as measured by urinary aMT6s. Our approach is to measure light levels (10-second intervals) and aMT6s (1-hour intervals, gold standard) for 72 hours following study enrollment; we will also collect exploratory measures of circadian rhythm, namely, actigraphy and heart rate. We will collect descriptive patient data to allow model adjustment during analysis. We define non-circadian ICU light patterns as abnormally low daytime light levels and abnormally high overnight light levels. We define circadian abnormalities as circadian misalignment and decreased circadian amplitude. The absence of circadian rhythm is an extreme decrease in amplitude (i.e., 100%). *This work will establish if non-circadian ICU light patterns are associated with the development of circadian abnormalities.*

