Research Design: We will enroll 100 subjects at increased risk for ICU delirium; subjects will be screened and consented as above. We will collect the following measures:

- a. **Room light levels** will be monitored from enrollment until Study D5 or until MICU discharge. We will set the light meter (HD450, Extech Instruments, New Hampshire) to read levels in lux at 10-second intervals. Meters will be placed in a standard location on the wall above the head of the bed as close as possible to eye level. Additional light measures will be taken adjacent to the patient's face (by holding the light meter next to their face for several seconds); these measures will be taken several times per day to assess light levels at or close to the eye.
- b. **Urinary aMT6s (1-hour intervals)** is the primary circadian measure for this aim. Melatonin is normally released just before habitual sleep time, and peak levels occur during sleep midpoint; urinary aMT6s peaks 2 hours after sleep midpoint.³⁸ For the proposed study, urinary aMT6s will be collected for 72 hours or until MICU discharge whichever occurs first. Urinary aMT6s will not be collected after MICU discharge. A 10mL aliquot of pooled urine sample collected every 1 hour will be used for analysis; total volume of urine will be recorded to allow for calculation of total aMT6s excreted. Total aMT6s excreted can be measured and is valid in patients with acute kidney injury, patients receiving diuretics,³⁹ and patients with decompensated cirrhosis.⁴⁰ We have the support of MICU nurse champions and the agreement of nursing leadership for the bedside nurse to collect these samples. Samples are stable at room temperature for 24 hours, will be transported to the lab daily, and stored at -80°C in the Translational Research Core. Samples will be batched and subsequently analyzed using a highly sensitive, competitive ELISA kit (IBL Laboratories, Germany).
- c. **Secondary measures** of actigraphy, surface body temperature, and continuous heart rate monitoring will be used in an exploratory manner. We plan to examine correlation with urinary aMT6s for use in future studies.

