Aim 1 Analytical Approach: Individual sleep midpoint will be calculated as halfway between habitual bedtime and habitual waketime as indicated during patient/surrogate interview questionnaire. Light dose will be calculated as the sum of mean lux per hour for each hour between 08:00 and 17:00 (day dose) and 22:00 and 06:00 (overnight dose). A day/night dose ratio will then be calculated by dividing the daytime light dose by the overnight light dose. Light dose ratio will be treated as continuous exposure variables, with higher numbers indicating a more favorable (circadian) exposure and lower numbers indicating a less favorable (non-circadian) exposure. Circadian alignment and amplitude will be calculated using time series analysis of urinary aMT6s using smoothing techniques to examine characteristics of circadian rhythm: acrophase (maxima) and nadir (minima). Statistical measures will evaluate for serial correlation, seasonality (periodicity), and trend. Longitudinal cosinor techniques will be used to test for alignment of nadir and acrophase with normal circadian phase and amplitude (e.g., individual sleep midpoint and estimated normal peak aMT6s).⁵⁵ The degree of misalignment versus normal will be recorded in minutes. The amplitude of the cycle will be defined as one-half of the difference between the acrophase and nadir and will be recorded in nanograms (ng) per hour.³⁰ Normal values have been identified for aMT6s.^{30,56} The assessment of circadian abnormalities for association with light patterns will be solely based on aMT6s analysis. Heart rate, iButton gradient readings, and actigraphy activity counts will be evaluated via cosinor techniques analogous to the aMT6s analysis described above. Actigraphy activity counts will also be evaluated by visual inspection of normalized mean activity per hour (Fig 3) and as described by Duclos et al.³² Confounder and effect modifier variables: Severity of illness will be calculated according to the APACHE II algorithm⁵⁷ and expressed as a continuous variable. Sepsis will be expressed as a categorical variable (absent, septic, septic shock) based on the sepsis-3 criteria.⁴⁷ The risk of OSA will be expressed as a categorical variable (low risk, high risk) based on the STOP-BANG algorithm.^{46,58} Overnight ICU care events per the timestamp data described above will be calculated as the number of ICU care events per hour between 22:00 and 06:00. Average daytime and overnight room temperature will be calculated as a continuous variable.

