
Testing for Associations: Because both measures of circadian abnormality (misalignment and decreased amplitude) are continuous and normally distributed, multivariable linear regression models will test for associations, with light dose ratio serving as the exposure. Linearity of the associations will be examined graphically, and higher order terms will be considered as necessary. Models will be adjusted for age, gender, severity of illness, sepsis, risk of OSA, ICU care events per hour, and room temperature variables. We will test for modification of the association between light dose ratio and the outcomes by sepsis and risk of OSA. Because of the non-trivial intra-correlation coefficient expected from the serial correlation of the repeated outcome measures over time, models will employ generalized estimating equations with an auto-regressive correlation structure. Model fit will be evaluated with residual analysis, and significance will be defined as a two-sided p-value ≤ 0.05 . Power Calculations. For both continuous, normally distributed outcomes, power calculations assume a two-sided alpha of 0.05, power of 90%, a sample size of 100, and prevalence of covariates ranging from 20% to 50%. For minutes of misalignment, we further assume a mean of 180 minutes with a standard deviation of 95 and for amplitude a mean of 450 ng with standard deviation of 180.³⁰ Under these assumptions, our sample of 100 is sufficient to detect a range of minimal average shifts between 52-65 minutes of misalignment, and 98-123 ng of urinary aMT6 per

incremental change in the explanatory variables.

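### The Aim 1 repeated-measures models have no study-day term, so in a patient-day analysis part of a shared day-to-day drift can be attributed to light

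*Combined protocol and SAP*

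**What the plan says.** Under Statistical Considerations, Aim 1, Testing for Associations, the light dose ratio is the exposure in multivariable linear models for misalignment and for amplitude. The covariates are listed: "Models will be adjusted for age, gender, severity of illness, sepsis, risk of OSA, ICU care events per hour, and room temperature variables". The outcomes are repeated: the text refers to the "serial correlation of the repeated outcome measures over time" and for that reason "models will employ generalized estimating equations with an auto-regressive correlation structure".

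The Aim 1 Analytical Approach defines the exposure: "A day/night dose ratio will then be calculated by dividing the daytime light dose by the overnight light dose". The day dose is a sum of hourly mean lux from 08:00 to 17:00, and the night dose a sum from 22:00 to 06:00. It does not say whether there is one ratio per day or one per patient.

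Time is mentioned once, in the step that characterises the aMT6s series: "Statistical measures will evaluate for serial correlation, seasonality (periodicity), and trend".

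Two design statements bear on the point. In the Aim 1 Research Design, "urinary aMT6s will be collected for 72 hours or until MICU discharge whichever occurs first". In the Timeline of Study Activities, "light measurement (part of feasibility) will start no later than 12:00 on D1".

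**The concern.** The light coefficient is the answer to Hypothesis 1. In a patient-day analysis it mixes two comparisons: patients with more or less favourable light on the same day, and later days with earlier days. Only the first is informative about light if the outcome also moves with time for other reasons, such as recovery or worsening after admission.

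A shared time course is plausible. All patients are enrolled within 30 hours of hospital admission, so study day closely tracks time since admission. The Aim 1 Rationale is framed around onset: "This work will establish if non-circadian ICU light patterns are associated with the development of circadian abnormalities". If the ratio also drifts by day, a model without study day can show a light association when there is none, or hide a real one. The bias can go in either direction.

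The autoregressive structure does not help. It describes the correlation of residuals within a patient and leaves a trend in the mean where it was.

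**Working it through.** **Plan's own figures.** The plan gives no daily trend in light or aMT6s, so there is no figure on this point to reproduce. The nearest yardstick is the stated detectable shift of 52 to 65 minutes. The simple formula (1.96 + 1.2816) × 95 / √(100·p(1−p)) gives 61.6 minutes at p = 0.5 and 77.0 at p = 0.2, so the stated range is not reproduced. That is a separate matter and is not used below.

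**Inputs from the plan.** 100 patients; misalignment mean 180 minutes, SD 95; at most 72 hours of aMT6s, so about three daily cycles; two-sided 0.05; median ICU stay 3 days.

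**Assumed inputs.** Within-patient correlation 0.5; true light effect zero; the trends given below.

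**Step 1: how much of a shared trend loads on light.** Take three cycles per patient, an AR(1) correlation of 0.5, and a ratio with unit SD, half of its variance between patients. Let the ratio shift by s SD per day and the outcome by δ minutes per day.
- Weight on the day trend: the centred days (−1, 0, 1) give 2/0.75 = 2.667.
- Weight on the remaining ratio variation: 0.5 × (1.25/0.75) + 0.5 × (3.25/0.75) = 3.0.
- Their quotient is 2.667/3.0 = 8/9.
- Bias per SD of ratio = (8/9)·s·δ / (1 + (8/9)·s²).
- Share of the trend attributed to light = (8/9)·s² / (1 + (8/9)·s²).

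| s (SD/day) | Share of trend | Bias at δ = 20 | Simulated bias at δ = 20 |
|---|---|---|---|
| 0.1 | 0.9% | 1.8 min | 1.9 min |
| 0.3 | 7.4% | 4.9 min | 5.1 min |
| 0.5 | 18.2% | 7.3 min | 7.2 min |

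If s or δ is zero, the bias is zero. In 2,000 simulated trials per setting, the test rejected in 16% (s = 0.3) and 31% (s = 0.5) at 20 min/day without day indicators, and in about 6% with them.

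**Step 2: false positives with the raw ratio and incomplete follow-up.** Patients have 1, 2 or 3 cycles with probability 0.2, 0.3 and 0.5. The log ratio has SD 0.5 between and 0.4 within patients. The models are GEE with an estimated AR(1) correlation and sandwich standard errors. Each setting was run several times with 800 to 1,500 replicates, so a rate near 14% has a simulation error of about √(0.14 × 0.86/1000) = 1.1 percentage points.

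| Light ratio | Shared change | No day term | Day term |
|---|---|---|---|
| Rises 20%/day | 10 min/day | 8–10% | 7–9% |
| Rises 20%/day | 20 min/day | 13–16% | 7–10% |
| Rises 20%/day | 30 min/day | 19–20% | 7–10% |

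A worsening of 20 min/day gives the same error with the opposite sign. The floor of 7 to 10% comes mainly from the skewed raw ratio, not from time.

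**Step 3: a shift that the plan itself can create.** A D1 recording that starts at 12:00 covers 5 of the 9 hours in the 08:00 to 17:00 window. A summed D1 day dose is then mechanically low.
- Noon start for everyone, ratio otherwise stable: 20–22% at 20 min/day and 33–36% at 30 min/day without a day term; 6–9% with it.
- Recorded D1 daytime hours spread evenly from 5 to 9: about 12–14% without; 7–10% with.
- Noon start with the dose divided by hours recorded: 8–9% without; 8–9% with. The effect is gone.

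**Step 4: one ratio per patient.** With a ratio that is constant within a patient, a 20 min/day trend gives 5.7% and no bias. With a per-patient average of the daily ratios, the rate is about 10% against 8–10%.

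**The case against.** The strongest reply is that the plan never says the ratio is computed daily. With one ratio per patient there is almost nothing to correct, so the visible gap is the unstated unit. That stands, and it is why the fix begins there. Repeated outcomes in a GEE make the patient-day reading natural, but do not settle it.

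The trends are also undocumented. The Aim 1 Rationale states a hypothesis about light and abnormality; it does not report a shared daily drift. Lighter overnight care after the first night is conjecture, and overnight care events per hour are already a covariate, so that route is partly adjusted. This stands too and limits the point to a risk.

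Safeguards exist in part. The trend check on the aMT6s series and the residual analysis could reveal a large drift. Neither pre-specifies a term in the association model.

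Three stronger readings are tempting and are not supported:
- A reader might infer that any change over the ICU stay would be credited to light. Only part of it is (about 1 to 18% in Step 1), only if both trends exist, and the window is at most 72 hours.
- A reader might take the 33–36% under a universal noon start as the size of the problem. The plan makes noon the latest start, and this component vanishes once the dose is normalised for hours recorded. It is mainly a partial-day dose problem.
- A reader might extend the point to Aim 3. The Aim 3 Analytical Approach specifies logistic regression and no per-cycle model.

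**Conclusion.** The omission is real: the listed adjustment set has no time term, and nothing else in the plan puts time into the mean model. Its effect is conditional on three things together: a day-specific light ratio, a shared daily change in the outcome, and a daily shift in the ratio. The documents establish none of these firmly. The late D1 start gives one documented route to the third.

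Under the assumed 20% per day rise in the ratio and 20 to 30 minutes per day shared change, the false-positive rate for Hypothesis 1 is about 14 to 20% without a day term and about 7 to 10% with it. At 10 minutes per day the gap is negligible. With one ratio per patient the bias is small or nil. This is a cheap improvement of minor severity, with no showing that the planned Aim 1 result would be wrong.

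**What to change.** In the Aim 1 Analytical Approach, state the unit of analysis for the light ratio and for both circadian outcomes: patient-day (or aMT6s cycle) or patient. If it is patient-day, add study day or aMT6s cycle number as a categorical covariate to both GEE models, misalignment and amplitude, so that the light coefficient compares patients on the same day. State also whether the light dose is divided by the hours recorded, because that removes the part of the D1 shift caused by a late start.

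The cost is a few sentences in the analysis plan, about two degrees of freedom, and a small loss of precision if there is no time trend. Study day is already recorded, so no new data are needed.

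### The Aim 1 detectable shifts are computed for a yes/no covariate (and at about 80% power), not for the continuous light dose ratio that tests Hypothesis 1

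*Combined protocol and SAP*

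**What the plan says.** Under Statistical Considerations, the Aim 1 Analytical Approach defines a day/night light dose ratio and fixes its scale: "Light dose ratio will be treated as continuous exposure variables". The Testing for Associations paragraph then makes that ratio the exposure: "multivariable linear regression models will test for associations, with light dose ratio serving as the exposure", adjusted for age, gender, severity, sepsis, OSA risk, care events and room temperature, with GEE for repeated outcomes.

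The Power Calculations text that follows covers both outcomes. It says that "power calculations assume a two-sided alpha of 0.05", with "power of 90%, a sample size of 100" and a "prevalence of covariates ranging from 20% to 50" percent. For misalignment it assumes "a mean of 180 minutes with a standard deviation of 95"; for amplitude, a mean of 450 ng and an SD of 180. It concludes that "our sample of 100 is sufficient to detect" shifts of 52-65 min and 98-123 ng per "incremental change in the explanatory variables".

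Neither document section gives an SD, a range or an increment for the light dose ratio, or a detectable slope for it.

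**The concern.** A prevalence describes how often a yes/no characteristic occurs; a continuous ratio has none. The power paragraph therefore appears to have been worked out for a variable such as high versus low OSA risk, which in Aim 1 is an adjustment variable and effect modifier, and then presented as the justification for the light-ratio analysis. The width of each printed range (52 to 65, 98 to 123) would reflect only the assumed prevalence and carry no information about light.

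This is the only sample-size justification for Aim 1. If it describes a different kind of variable, a reader cannot tell from it what strength of association between light and circadian disruption the cohort can detect.

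**Working it through.** **Inputs (all from the Aim 1 Power Calculations text).** N=100; two-sided alpha 0.05; power 90%; prevalence p from 0.20 to 0.50; outcome SD 95 min and 180 ng. A 0/1 variable has SD sqrt(p(1-p)): 0.50 at p=0.5 and 0.40 at p=0.2.

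**Step 1. Do the printed ranges come from a yes/no variable?** For a 0/1 covariate the detectable difference is proportional to 1/sqrt(p(1-p)), so going from p=0.5 to p=0.2 multiplies it by 0.50/0.40 = 1.25. The plan's ranges give 65/52 = 1.250 and 123/98 = 1.255. They carry that signature.

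**Step 2. Reproduce the printed figures.** Regression slope t-test with 98 df. Solve for the correlation r at which a noncentral t with noncentrality sqrt(N) x r/sqrt(1-r²) reaches the required power. Then, reading 95 and 180 as total SDs, the difference is r x SD / sqrt(p(1-p)).

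| Power | r | min, p=0.5 | min, p=0.2 | ng, p=0.5 | ng, p=0.2 |
|---|---|---|---|---|---|
| Plan (states 90%) | – | 52 | 65 | 98 | 123 |
| 80% | 0.2723 | 51.7 | 64.7 | 98.0 | 122.5 |
| 90% | 0.3111 | 59.1 | 73.9 | 112.0 | 140.0 |

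All four printed figures return to rounding at 80% power. At the stated 90% none does, by this method or by the others tried:

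- two-group normal approximation: 61.6-77.0 min, 116.7-145.9 ng;
- Fisher z: 60.4-75.5 min, 114.4-143.0 ng;
- one-sided slope test: 53.7-67.1 min.

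Power at the printed shifts is about 80% by the slope test and about 78% by the two-group approximation.

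**Step 3. What the printed figures imply per SD of exposure.** 52 x 0.5 = 26.0 and 65 x 0.4 = 26.0 min; 98 x 0.5 = 49.0 and 123 x 0.4 = 49.2 ng. Read as slopes per unit of the light ratio, they would hold only if the ratio had an SD of 0.4-0.5, which the plan does not state.

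**Step 4. The figure for the continuous exposure.** N=100, two-sided 0.05, 90% power, one value per patient, no adjustment:

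- Total SD: 0.3111 x 95 = 29.6 min; 0.3111 x 180 = 56.0 ng/h per SD of the ratio.
- Residual SD: half of the p=0.5 two-sample t result, 62.2 x 0.5 = 31.1 min; 117.9 x 0.5 = 58.9 ng/h per SD.

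A per-unit slope needs the SD of the ratio. With assumed SDs of 0.5, 1, 2 or 5, the total-SD slopes are 59, 30, 15 or 6 min per unit and 112, 56, 28 or 11 ng/h per unit.

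**Step 5. Allowance for covariates (assumption; the plan gives no value).** If the covariates explain a share R² of the ratio, multiply by 1/sqrt(1-R²). For R² = 0.2 and 0.3: 29.6/sqrt(0.8) = 33.1 and 29.6/sqrt(0.7) = 35.4 min; 56.0/sqrt(0.8) = 62.6 and 56.0/sqrt(0.7) = 66.9 ng/h. This is before any offset from outcome variance explained by the same covariates.

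**The case against.** The wording about an incremental change in the explanatory variables is plural and vague. The sponsor could say that it was never a claim about one unit of the light ratio, and that the figures concern binary covariates such as OSA risk. The first part stands: the text is ambiguous, not a stated slope per ratio unit. The second does not rescue the paragraph, because on that reading nothing is said about the exposure in Hypothesis 1. The Aim 2 power paragraph does define its increments (60 minutes, 100 ng); Aim 1 has no counterpart.

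A fair objection also applies to any replacement figure. It depends on whether 95 and 180 are total or residual SDs. The plan gives them beside the outcome means, which reads as total, and the total-SD convention is the one that reproduces the printed values. An allowance for covariate correlation is one-sided unless it also credits the outcome variance those covariates explain; if they explained equal shares of ratio and outcome, the two effects would roughly cancel. The planned GEE with repeated outcomes is not represented, and the plan gives no inputs for it. These points limit the precision of the replacement but leave the mismatch in place.

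Two stronger readings should be resisted. A reader might set 26 min per SD beside 30 or 31 and conclude that a continuous exposure costs sensitivity. It does not: 26 is an 80%-power, total-SD value, and the gap comes from the power level and the SD convention. A reader might also infer that the cohort is too small, since 90% power for the printed shifts would need about 132-134 patients by the slope test. But those shifts describe a yes/no covariate, and the plan names no minimum effect of light that the study must detect.

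**Conclusion.** The point holds as a misdirected power statement. The 52-65 min and 98-123 ng shifts follow from a yes/no covariate with 20-50% prevalence, while the tested exposure is continuous with no stated SD or increment, so they do not give the detectable effect for Hypothesis 1. The same figures correspond to about 80% power, not 90%, if 95 min and 180 ng are total outcome SDs. Correcting the power level alone would still leave a figure for the wrong kind of variable.

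For the ratio itself, N=100 supports a detectable correlation of about 0.31 at 90% power: about 30 min or 56 ng/h per SD (total SDs), or 31 min or 59 ng/h (residual SDs). This rests on one value per patient, no covariate adjustment and a linear association. The documents do not support the conclusion that N=100 is inadequate, and no planned analysis or estimate changes.

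**What to change.** Rewrite the closing part of the Aim 1 Power Calculations text:

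- State the detectable slope per SD of the light dose ratio: N=100, two-sided alpha 0.05, 90% power, one value per patient, unadjusted; correlation about 0.31; about 30 min or 56 ng/h per SD if 95 and 180 are total SDs (31 min or 59 ng/h if residual).
- Say which SD convention is used.
- Label any allowance for covariate correlation as an assumption. For example, R² of 0.2-0.3 gives 33-35 min or 63-67 ng/h with total SDs, before any offset from outcome variance that the covariates explain.
- Note that the GEE repeated measures are not modelled in the calculation.
- Delete the prevalence range, or label it as applying only to yes/no covariates and correct its figures to 90% power (59-74 min, 112-140 ng, total SDs).

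The cost is the rewording of one paragraph. It needs no extra patients, no new data and no change to the analysis.

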- a. **Setting:** The study site is the medical intensive care unit (MICU) at Yale-New Haven Hospital (YNHH), York Street Campus and St. Raphael's Campus. Median ICU stay is 3 days. Predominant reasons for admission are sepsis and acute respiratory failure. MICU rooms are private. There is currently a unit-wide sleep promotion protocol which limits care activities from 00:00 to 04:00.
- b. **Design:** Aim 1 and 2, prospective cohort study; Aim 3 pilot randomized controlled trial (RCT). Aim 3 which is not dependent on Aims 1 and 2 will be conducted first.
- c. **Cohort:** We will enroll 100 subjects at risk for ICU delirium. In addition, we will enroll 16 subjects into the pilot randomize control trial.
- d. **Inclusion and exclusion criteria:** This study will focus on adults at an increased risk for ICU delirium. We have selected age ≥ 50 years as an inclusion criteria to study middle-aged to older adults who are at increasing risk for delirium while not overly restricting our sample. We will not restrict patients based on admission severity of illness (APACHE II) because we think this is a critically important confounder and would like to study the effect of the full spectrum of severity of illness on our outcomes. We will exclude patients at significant risk for pre-existing circadian abnormalities (e.g. shift work). We will also exclude patients with co-morbid disease or medication use that makes measurement of urinary aMT6s or actigraphy unreliable. Table 2 lists inclusion and exclusion criteria.

Table 2: Inclusion Criteria	Exclusion Criteria

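### Aim 1's printed detectable shifts (52-65 min; 98-123 ng) have about 80% power under the stated inputs, not the stated 90%

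*Combined protocol and SAP*

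**What the plan says.** The Power Calculations text under Statistical Considerations, Aim 1, covers both continuous outcomes. It assumes two-sided alpha 0.05 and "power of 90%, a sample size of 100, and prevalence of covariates ranging from 20% to 50" per cent. For the outcomes it takes "a mean of 180 minutes with a standard deviation of 95 and for amplitude a mean of 450 ng with standard deviation of 180". On those assumptions it states that "our sample of 100 is sufficient to detect a range of minimal average shifts between 52-65 minutes of misalignment, and 98-123 ng" can be detected per "incremental change in the explanatory variables".

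Three other statements bear on the calculation:

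- Aim 1 Analytical Approach, on the exposure: "Light dose ratio will be treated as continuous exposure variables".
- Testing for Associations, on the analysis: "models will employ generalized estimating equations with an auto-regressive correlation structure".
- Aim 1 Research Design, on the outcome data: "urinary aMT6s will be collected for 72 hours or until MICU discharge whichever occurs first". Under Project Overview, Setting: "Median ICU stay is 3 days".

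The power inputs include no R-squared for covariates, no within-patient correlation and no number of repeated values.

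**The concern.** The paragraph ties its result to a closed list of inputs, so it can be checked, and the printed shifts look too small for 90% power with 100 participants. This is the only power justification for the Aim 1 cohort, which Aim 2 reuses. If the true figure is about 80%, someone reading a null result would take the risk of a missed effect to be 10% when the plan's own inputs put it near 20%.

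The calculation also uses a prevalence, so it describes a contrast between two groups. The exposure of interest is a continuous ratio, and the size of its increment is not defined.

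**Working it through.** **Inputs** (all from the Aim 1 power paragraph): two-sided alpha 0.05; N = 100; prevalence p = 0.5 or 0.2; SD = 95 min or 180 ng.

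**Formula.** For a shift d in a binary factor, the noncentrality is λ = d·√(N·p(1−p))/s.

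- SD read as residual: s = SD.
- SD read as the total outcome SD: s² = SD² − p(1−p)d².

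Solving for d gives d = K·SD/√(N·p(1−p)), with K = λ (residual) or K = λ/√(1 + λ²/N) (total). Here √(N·p(1−p)) is 5 at p = 0.5 and 4 at p = 0.2, so SD/√(N·p(1−p)) is:

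- 95/5 = 19 and 95/4 = 23.75 min
- 180/5 = 36 and 180/4 = 45 ng

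**Reproducing the printed figures.** The t test with 98 df needs λ = 2.829 for 80% power and 3.274 for 90%. The normal approximation needs 2.802 and 3.242. The four columns are min at p = 0.5, min at p = 0.2, ng at p = 0.5 and ng at p = 0.2.

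| Power | SD reading, test | min, 0.5 | min, 0.2 | ng, 0.5 | ng, 0.2 |
|---|---|---|---|---|---|
| Printed (90% stated) | | 52 | 65 | 98 | 123 |
| 80% | total, t | 51.73 | 64.66 | 98.01 | 122.51 |
| 80% | total, normal | 51.26 | 64.07 | 97.12 | 121.40 |
| 80% | residual, t | 53.76 | 67.20 | 101.86 | 127.32 |
| 80% | residual, normal | 53.23 | 66.54 | 100.86 | 126.07 |
| 90% | total, t | 59.11 | 73.89 | 112.01 | 140.01 |
| 90% | total, normal | 58.59 | 73.23 | 111.01 | 138.76 |
| 90% | residual, t | 62.20 | 77.75 | 117.86 | 147.32 |
| 90% | residual, normal | 61.59 | 76.99 | 116.69 | 145.87 |

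The total-SD t test at 80% rounds to all four printed values, and no other row does. No 90% row gives any of them. Two further variants also miss: a Fisher-z calculation at 90% (60.4-75.5 min; 114.4-143.0 ng) and one-sided alpha 0.05 at 90% (53.7-70.0 min; 101.8-132.6 ng across variants).

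**Power at the printed shifts.** For 52 min with total SD, s² = 9025 − 0.25 × 2704 = 8349, so s = 91.37 and λ = 52 × 5/91.37 = 2.845, giving 80.4%. With residual SD, λ = 260/95 = 2.737, giving 77.3%. For 52/65/98/123:

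- total SD: 80.4/80.4/80.0/80.3% (t) or 81.2/81.2/80.8/81.1% (normal)
- residual SD: 77.3/77.3/76.9/77.2% (t) or 78.1/78.1/77.7/78.0% (normal)

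**N for 90% at the printed shifts.** Total SD: 130-134. Residual SD: 141-144.

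**Variance factor that would restore 90% at N = 100.** 0.747-0.771 (total) or 0.691-0.713 (residual), a reduction of roughly 23-31%.

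**Continuous exposure.** Per SD of the light dose ratio, d = K·SD/√N (total SD, t test, before covariate adjustment). At 90% power, K = 3.111, giving 29.6 min and 56.0 ng. At 80%, K = 2.7225, giving 25.9 min and 49.0 ng.

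**Aim 2 (secondary).** Its power paragraph gives risk ratios of 1.12 per 60 min and 1.08 per 100 ng for 80 participants but no exposure SD, so they cannot be checked. As an illustration only, assume the Aim 1 SDs, 100 ng referring to amplitude, 3 days as the rate at mean exposure, and a variance factor of 1.2. Then SE(log RR) = √(1.2/(80 × 3 × s²)), with s = 95/60 or 180/100, which is 0.0447 or 0.0393. Power is about 72% for 1.12 and 50% for 1.08; 90% power corresponds to about 1.16 and 1.14.

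**The case against.** The strongest reply is that the power statement may include a variance reduction that the text omits. The planned analysis adjusts for covariates and uses repeated values per patient. If the quoted SDs describe a single daily value, averaging two values with correlation 0.5 gives a variance factor of (1 + 0.5)/2 = 0.75. Three values with first-order autoregressive correlation 0.7 give (3 + 4 × 0.7 + 2 × 0.49)/9 = 0.753. Both correlations are assumptions, but not extreme ones.

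The match at 80% is also less conclusive than four agreeing figures suggest. All four are the same multiplier K applied to 19, 23.75, 36 and 45, so they carry essentially one piece of information. A covariate R-squared of 0.25 (total SD, t test) gives 51.83, 64.78, 98.20 and 122.74 at 90% power, and 0.29 (residual SD, normal) gives 51.90, 64.87, 98.33 and 122.91. Both round to the printed values.

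What stands is that mislabelling is not proven, and that the planned analysis may have more than 80% power. What does not stand is the paragraph as written: it presents its result as following from listed inputs, and no such reduction is among them.

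It can also be said that N = 100 is an input, that the plan sets no minimum important difference, and that the models contain categorical terms for which a prevalence makes sense. These points limit the consequences but leave the arithmetic unchanged. The Aim 2 illustration rests on several assumptions: with the same formula, exposure SDs of about 121 min and 298 ng would give 90% power at the printed ratios. It is not evidence of an error there.

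**Conclusion.** The concern holds. On the stated inputs the printed Aim 1 shifts have 77-81% power, not 90%, so the type II error is 19-20% (total SD) or 22-23% (residual SD). This rests on the listed alpha, N, prevalences and SDs, with no variance reduction. The gap of about 10 points or more far exceeds any difference between the t and normal calculations.

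That an 80% calculation was labelled 90% is the simplest explanation, but it remains an inference. The undefined increment for the continuous exposure is a separate gap in the same paragraph. For Aim 2 the only firm statement is that the exposure SDs are missing. The point should be fixed, but it concerns the cohort aims only.

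**What to change.** In the Aim 1 power paragraph, do one of the following and say whether the SDs are total or residual:

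1. Keep the printed shifts and state the power as about 80% (about 77-78% if the SDs are residual).
2. Keep 90% and restate the shifts as about 59-74 min and 112-140 ng (total SD) or 62-78 min and 117-147 ng (residual SD).
3. If a covariate or repeated-measures gain was used, state it and show that it reproduces the printed figures. Include the number of daily values assumed per patient, since urine collection ends at MICU discharge and the median ICU stay is 3 days.

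In each case, say that the shifts apply to a binary factor. A useful addition is the detectable effect per SD of the light dose ratio: about 30 min and 56 ng at 90% power, or 26 min and 49 ng at 80%, with total SD and before adjustment. In Aim 2, add one line giving the exposure SDs used.

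The cost is a text edit. Enrolment, analysis and conduct do not change.
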